However, such a resource is vital to the effective management of future pandemics, and later waves of the current pandemic. The establishment of a permanent biobank in Ireland that can be enabled legally, and established with suitable funding, needs serious consideration now, in parallel with this work.

We have successfully used other methods to perform serosurveys in the past in Ireland, such as the Hepatitis C population prevalence study (4), studies to determine the prevalence of bloodborne viruses amongst Irish prisoners (5) and Phase 2 of the European Sero-Epidemiology Network (ESEN 2), which examined the level of population immunity to a variety of vaccine preventable diseases (measles, mumps, rubella, pertussis, diphtheria, varicella zoster, hepatitis A and hepatitis B)(6).

Having reviewed approaches to sero-epidemiological studies being undertaken internationally, including attending an WHO teleconference on serosurveillance studies on 15th April, and subsequent participation in the ECDC/WHO Europe sero-prevalence collaborative group, our view is that the World Health Organization (WHO) population-based age-stratified sero-epidemiological investigation protocol for COVID-19 virus infection, adapted for use in the Irish population, provides a suitable methodology. In their protocol WHO indicate that each country may need to tailor some aspects of the protocol to align with context-specific factors including public health, laboratory and clinical systems, capacity, availability of resources and cultural appropriateness. The protocol is available at <https://www.who.int/publications-detail/population-based-age-stratified-seroepidemiological-investigation-protocol-for-covid-19-virus-infection>

The WHO aim is that the studies are carried out using standardised methodology and serological tests, enabling comparison of results between countries, and pooling of results, thereby building international knowledge.

Aims

The aims of this study are:

1. to calculate the anti-SARS-CoV-2 IgG seroprevalence in two areas in Ireland, representing high and low incidence areas, in order to estimate the cumulative exposure to SARS-CoV-2 infection to date, by sex and age group
2. To estimate the fraction of asymptomatic, pre-symptomatic or subclinical infections in the population and by sex and age group

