Statistical advice has been obtained from the CSO on the appropriate sample size. For the serological part of the study, a sample size of 1,000 in the 12-69 years Sligo population and 1,600 in the 12-69 years Dublin population will be required to calculate overall prevalence rates with the required level of precision.

The numbers invited to participate will be double this number (i.e. 2,000 and 3,200 in Sligo and Dublin respectively) in order to achieve the required sample size, to allow for non-response and for people who will be ineligible due to self-isolating or being ill with COVID-19 at the time of the study..

Participant recruitment and data collection

Each randomly selected individual will be contacted by letter by the HSE HPSC asking them if they would like to take part in the study. For children aged 12-17 years, the child's assent, as well as the parent/guardian's consent will be sought. An information leaflet describing the study will accompany the letter. They will also be advised that they may get further information on the study website or by phoning the research team on a helpline. They will be asked to reply, by text, email, or phone call, indicating their interest in the study and providing their phone number. Those indicating an interest in the study will be phoned by a member of the research team.

One reminder letter will be sent by HSE to non-responders after an interval of two weeks from the initial letter.

If they consent to take part in the study, they will be asked to complete a short questionnaire by phone and will also receive an appointment at a time convenient to them to visit the location where blood sampling will be undertaken. A unique study ID number will be allocated to each person by HSE HPSC.

Inclusion and exclusion criteria

This study aims to be as representative of the Irish population in the selected areas (Dublin and Sligo in the first round) as possible. Everyone in these areas who is registered on the PCRS system, in the age group 12 to 69 years, and who is selected for the study will be eligible to complete the questionnaire. The invitation letter will include information in several languages to indicate to

recipients that interpretation services are available if required and how to access them. HSE interpretation services will be used to provide information for these individuals.

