Repeat serum samples (at 3 months, 6 months and 12 months) on those who are SARS-CoV-2 IgG positive will be tested.

Retention of biological materials

Samples will be stored in the NVRL for a period of 2 years. The serology assays for SARS-CoV-2 are in the early stages of development and it is possible that more sensitive and specific antibody tests and antibody function tests will be developed in the coming months. The retained samples may be retested by the research team during these 2 years. The consent form will specifically ask the participant for consent for their blood sample to be stored in NVRL for up to 2 years, on the understanding that during this time it may be tested again for antibodies and antibody function by the study’s research team. After 2 years they will be destroyed.

Data analysis

Response rates and eligibility rates will be calculated. The demographic and other characteristics of the study participants, obtained from the questionnaires, will be analysed and compared to the general population where appropriate to assess their representativeness.

The antibody results, age, sex and geographic area of all participants will be used to calculate an overall prevalence of antibodies to SARS-CoV-2, with a 95% confidence interval, in the sampled populations. This can be used to estimate the number of persons seropositive in the two study population areas. Acknowledging the limitations of having only two geographical areas representing categories of incidence, we will produce corresponding Irish population estimates using weighted analyses. The relationship between the presence of antibodies to SARS-CoV-2 and reported symptoms or previous diagnosis of COVID-19 will be examined.

For participants included in the serial sampling study, we will calculate the proportion for whom antibodies are still detected at each subsequent sampling time point. The relationship between

antibody kinetics and reported symptoms or previous diagnosis of COVID-19 will be examined alongside other participant characteristics such as age.

Reporting of the results

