Individual results of the blood test will be provided to participants by letter, explaining that the result is not a diagnostic test, and is meaningful at a population rather than individual level. They will be advised that the presence of antibodies may not equate to immunity from future SARS-CoV-2 infection as further research is required to enhance our understanding of this disease, including the extent to which prior infection confers immunity. They will be advised to continue to follow all social distancing and hygiene measures recommended by the government

The potential benefits and harms of providing feedback to individuals were weighed up and on balance it was felt that feedback on presence of Ab to SARS-CoV-2 was appropriate as it would provide the person with knowledge that they had been infected and that it would be carefully explained to the person that the implications of that finding for re-infection was uncertain at this time. Participants will also be given the 'right not to know' and can specify at time of providing consent to participate to not receive their results.

Participants will be advised that they may phone a public health doctor member of the study team if they have queries about the result and will be provided with a contact phone number.

The participant's GP will also be provided with the result, if the participant has agreed to this.

Anonymised results will be shared with NPHE to inform the national pandemic response. In the interests of openness and transparency, a report on the study results will also be shared with the general public, via the HSE and HSE HPSC websites.

The HSE HPSC, through its role as IHR focal point for Ireland, will also share anonymised results with the World Health Organization (WHO) to add to global knowledge on the spread of COVID-19.

A manuscript outlining the study methodology, the results and their interpretation will be submitted for publication in a peer reviewed scientific journal

Those participants with detectable antibody to SARS-CoV-2 will also be invited to take part in a follow up study to determine if these antibodies are persistent 3, 6 and 12 months after the initial samples were taken and if they developed symptoms consistent with COVID-19 during this time. They will be asked for consent to take part in this study when results of the first round of testing are available. They will not be provided with the results of these further tests.

Repeat cross sectional survey

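### The Data analysis section names no adjustment of prevalence for assay sensitivity and specificity, which could materially distort the estimate in the low-incidence area

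*Protocol*

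**What the plan says.** Under Aims, the protocol will measure IgG seroprevalence in a high-incidence and a low-incidence area "in order to estimate the cumulative exposure to SARS-CoV-2 infection to date, by sex and age group". The quantity wanted is therefore past infection, not test positivity as such.

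Under Data analysis, "The antibody results, age, sex and geographic area of all participants will be used to calculate an overall prevalence of antibodies to SARS-CoV-2". The estimate is to carry an interval at the 95% level. The same paragraph then scales the result up: "This can be used to estimate the number of persons seropositive in the two study population areas". Weighted national estimates follow. The named inputs are the test result, age, sex and area. Se and Sp are not named, and the method for the interval is not given.

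The protocol treats the assay as imperfect. Under Retention of biological materials it says "The serology assays for SARS-CoV-2 are in the early stages of development" and allows for retesting with better assays. Under Laboratory testing, the assay will be chosen using manufacturer data, an independent assessment and verification at the reference laboratory. Those data are mentioned for selecting the assay and are not carried into the analysis.

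Under Sample size, "a sample size of 1,000 in the 12-69 years Sligo population and 1,600 in the 12-69 years Dublin population will be required". Sampling procedure designates Sligo as the low-incidence area in the first round.

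**The concern.** A crude proportion positive mixes true positives with false positives and leaves out infected people whom the test misses. When few people have been infected, nearly everyone tested can contribute a false positive, so even a small false-positive rate can rival the true signal. The study includes a low-incidence area by design, which is where this matters most.

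Three results are exposed. The Sligo prevalence may be off by an amount comparable with its own sampling error, and an interval based on survey sampling alone would not show it. The Dublin/Sligo comparison, a stated objective, would be pulled towards equality where false positives dominate. The scaled-up counts, national estimates and age-specific susceptibility would inherit the error.

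**Working it through.** **Inputs from the protocol.** Tested: 1,000 in Sligo and 1,600 in Dublin (Sample size). Interval level: 95% (Data analysis).

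**Inputs assumed, because the protocol gives none.** Se 90%; Sp 98% to 99.8%; true prevalence p of 1% in Sligo and 3% in Dublin, with other values of p as a check.

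**The plan's own figures.** The invited numbers reproduce: 1,000 × 2 = 2,000 and 1,600 × 2 = 3,200. The 1,000 and 1,600 cannot be reproduced, because neither the expected prevalence nor the target precision is stated.

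**Step 1. Expected crude estimate.** q = p·Se + (1 − p)(1 − Sp).
For Sligo with p = 1% and Sp = 99%: 0.01 × 0.90 + 0.99 × 0.01 = 0.0090 + 0.0099 = 0.0189. Among 1,000 people that is about 9 true and 10 false positives.

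**Step 2. Coverage.** This is the probability, with the number of positives distributed Binomial(n, q), that the unadjusted 95% interval contains p. The protocol does not fix the interval method, so the range over Wald, Wilson and exact (Clopper-Pearson) intervals is also shown.

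| Sligo, n = 1,000, p = 1%, Se 90% | Sp 98% | Sp 99% | Sp 99.5% | Sp 99.8% |
|---|---|---|---|---|
| Expected crude estimate | 2.88% | 1.89% | 1.40% | 1.10% |
| Coverage, exact interval | 1% | 39% | 83% | 96% |
| Coverage, range of three methods | 1–2% | 30–48% | 76–88% | 94–96% |

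For scale, at Sp 99% the bias is 1.89 − 1.00 = 0.89 points. The sampling half-width at q = 1.89% is 1.96 × √(0.0189 × 0.9811/1,000) = 0.84 points.

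**Step 3. Other prevalences, Sligo, Se 90%, Sp 99%.**
- p = 0.5%: crude 1.45%, coverage 9–22%.
- p = 2%: crude 2.78%, coverage 57–71%.
- p = 5%: crude 5.45%, coverage 89–92% (exact interval 91%).

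**Step 4. Area comparison, true 3% against 1% (ratio 3.0), Se 90%.**
- Sp 99%: Dublin 0.03 × 0.90 + 0.97 × 0.01 = 3.67%; ratio 3.67/1.89 = 1.9. Exact coverage for Dublin is 70%.
- Sp 99.5%: 3.19/1.40 = 2.3.
- Sp 99.8%: 2.89/1.10 = 2.6.

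**Step 5. Direction.** Bias = (1 − p)(1 − Sp) − p(1 − Se). At Se 90% and Sp 99.8%:
- p = 2%: 0.00196 − 0.00200 ≈ 0 (crude 1.996%).
- p = 3%: 0.00194 − 0.00300 = −0.00106 (crude 2.89%, too low).

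**Step 6. Effect of adjusting.** The Rogan-Gladen estimator is (q + Sp − 1)/(Se + Sp − 1). For Sligo at Sp 99%: (0.0189 − 0.01)/0.89 = 0.0100, so the true 1% is recovered. The half-width becomes 0.84/0.89 = 0.95 points, an approximate interval of 0.05% to 1.95%. This treats Se and Sp as known; it widens once their uncertainty is included.

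**The case against.** The strongest objection is that the protocol is silent rather than wrong. Data analysis is a short outline listing participant-level variables. It does not say that results will be left uncorrected, the assay had not been chosen, and a statistical analysis plan that is not shown may contain an adjustment. It would be wrong to infer that the sponsor has rejected correction. No weight is placed on the Bias and limitations section, since the available copy may be incomplete. What remains is that the protocol does name the inputs to its main estimate. Those inputs give a crude proportion, while the aim is cumulative exposure. Whether the main result is crude or test-adjusted defines what is being estimated, and it can be settled without knowing the Se and Sp values.

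The second objection is that the size rests on assumed figures. That is right, and it limits the claim. A reader might infer that the Sligo interval will usually miss the truth. In these calculations, coverage falls below 50% at p of 1% or less with Sp of 99% or lower, or at p of 2% with Sp of 98.5% or lower. Elsewhere it can be near nominal. A reader might also infer that the estimate is always too high; Step 5 shows that it need not be.

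Third, under Reporting of the results, feedback is justified partly because "it would provide the person with knowledge that they had been infected", while letters will say the result is not diagnostic. A reader might take this as a product of the same omission. It is not: the phrase is a rationale for offering feedback, not the letter's text, and adjusting prevalence changes no individual result. It forms no part of this point.

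Finally, the adjustment can be made at analysis without loss of data, and stored sera can be retested. Both lower the cost of the remedy, but neither puts an adjustment into the stated analysis.

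**Conclusion.** The point holds in conditional form. As written, the Data analysis section produces a crude prevalence and names no adjustment for Se and Sp, although the protocol concedes that the assays are immature and will have performance data reviewed. If Se is 90% and true Sligo prevalence is 1%, the expected crude figure runs from 1.1% (Sp 99.8%, exact coverage 96%) to 2.9% (Sp 98%, coverage 1%). Near-doubling requires a false-positive rate about equal to prevalence, as at 1% and Sp 99%. At 5% prevalence and Sp 99% the crude figure is 5.45% with coverage of 91%. All prevalence, Se and Sp values are assumptions. Because the protocol fixes neither the assay nor an expected prevalence, it gives no basis for presuming the favourable case.

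**What to change.** In Data analysis, define the main estimate for each area, and for each age and sex group, as test-adjusted prevalence: (apparent + Sp − 1)/(Se + Sp − 1), truncated to 0–1. Take Se and Sp for the chosen assay from the laboratory verification and independent validation data, and record the numbers of known positive and negative samples behind them. Use a 95% interval that carries both survey sampling error and uncertainty in Se and Sp, for example by bootstrap or a joint Bayesian model. Report the crude figure alongside. Derive the area comparison, scaled-up counts and national estimates from the adjusted figures.

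The cost is a few sentences in the protocol or analysis plan and a few lines of code, with no extra samples. Intervals will be wider (0.95 against 0.84 points in the Sp 99% example, before assay uncertainty is added), and the headline figure may be lower. Some small age and sex groups may be truncated at zero, which the report should state.

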Separate consent will be obtained, from participants who have antibodies to SARS-CoV-2 detected, and who agree to take part in the second study for data collection and processing, at 3, 6 and 12 months, for sample storage for 2 years, and for international sharing of the data with WHO (in an anonymised format)

Sample collection and processing

Sample testing locations will be established by the HSE in the two selected areas where the study is being undertaken. Options for suitable sites are currently under investigation. The sites will not be centres currently used for testing patients for possible current COVID-19 infection.

On arrival at the test centre, the team (administrative personnel and nurse phlebotomists) will confirm that the person is registered as a participant in the study, and will obtain written consent for sampling. Demographic details will be confirmed. A venous serum sample of 10mls will be collected

from each person by the nurse phlebotomist. Arrangements will be made for the participant to receive reimbursement for travel expenses incurred.

Specimens will be transported to the National Virus Reference Laboratory (NVRL) at 4 degrees Centigrade for testing using registered couriers. Consent forms will be sent to HSE HPSC where they will be scanned and entered into the secure database. The paper copies will then be securely shredded.

Those participants with detectable antibody to SARS-CoV-2 will also be invited to take part in a follow up study to determine if these antibodies are persistent 3, 6 and 12 months after the initial samples were taken and if they developed symptoms consistent with COVID-19 during this time. They will be asked for consent to take part in this study when results of the first round of testing are available. They will not be provided with the results of these further tests.

Laboratory testing

The SARS-CoV-2 IgG assay to be used by the NVRL will be selected based upon the antigenic targets utilised in the test, review of data generated by the manufacturer and independent assay assessment and also assay verification performed at the NVRL. It is probable, based upon the anticipated numbers for testing, that an automated platform will be used.

The format for the current assays is not suitable for the accurate investigation of SARS-CoV-2 IgG in samples collected “non-invasively” such as oral fluid. However, if a suitable test is identified this approach will be considered and a study amendment will be sought.

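### The antibody-persistence proportion is taken over baseline positives with no stated confirmation step, so it mixes false positives with true antibody loss and is likely biased downward

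*Protocol*

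**What the plan says.** Sample collection and processing sets the entry rule: "Those participants with detectable antibody to SARS-CoV-2 will also be invited to take part in a follow up study". Positives are invited, and they join only if they give separate consent (Informed consent).

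Laboratory testing leaves the assay open: "The SARS-CoV-2 IgG assay to be used by the NVRL will be selected based upon the antigenic targets utilised in the test", together with manufacturer data, independent assessment and verification at the reference laboratory. On follow-up it says: "Repeat serum samples (at 3 months, 6 months and 12 months) on those who are SARS-CoV-2 IgG positive will be tested".

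The measure is fixed under Data analysis: "we will calculate the proportion for whom antibodies are still detected at each subsequent sampling time point". The same section plans to relate antibody kinetics to symptoms, previous diagnosis and characteristics such as age.

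On assay maturity, Retention of biological materials says: "The serology assays for SARS-CoV-2 are in the early stages of development". On further testing it says: "The retained samples may be retested by the research team during these 2 years". That retesting is optional and is not linked to entry or to the persistence proportion.

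**The concern.** The persistence proportion is meant to describe what happens to SARS-CoV-2 antibody over 3, 6 and 12 months. Its denominator is everyone in the serial study, and they are there because of a positive baseline result. Some of those results will be false. A false positive that is negative at follow-up looks exactly like antibody loss, and one caused by stable cross-reactivity looks like persistence. Neither carries information about SARS-CoV-2 antibody.

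One area in each round is chosen for low incidence, where the share of false results among positives is highest. Follow-up samples are taken only from positives, so the study has no group that would show how often false reactivity disappears. Correcting the area prevalence for assay error would not help, because that correction does not identify which individuals are false positives.

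At stake is the third aim, antibody kinetics. The estimate could suggest faster loss than is real. The comparison by symptoms could show a difference that is an artefact, since false positives are likely to sit mostly among people without symptoms.

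**Working it through.** **The plan's own figures.** The protocol gives no expected size for the serial cohort and no persistence figure, so there is nothing to reproduce on this point. The numbers tested come from Sample size: 1,000 in Sligo and 1,600 in Dublin.

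**Assumed inputs (not in the protocol).** Baseline sensitivity 90%. Specificity 99%, 99.5% or 99.9%. Prevalence 1% in Sligo and 5% in Dublin. Share of true positives still reactive at follow-up, T = 95%. Share of false positives still reactive, k = 0, 0.5 or 1. True and false positives consent equally often.

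**Formulas.** True positives TP = n × prevalence × 0.90. False positives FP = n × (1 − prevalence) × (1 − specificity). Observed persistence = (TP × T + FP × k) / (TP + FP).

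**Counts.** TP = 1,000 × 0.01 × 0.90 + 1,600 × 0.05 × 0.90 = 9 + 72 = 81. At 99% specificity, FP = 990 × 0.01 + 1,520 × 0.01 = 9.9 + 15.2 = 25.1. At 99.5% it is 12.55, and at 99.9% it is 2.51. True positives still reactive: 81 × 0.95 = 76.95.

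| Specificity | Positives | False share | k = 0 | k = 0.5 | k = 1 |
|---|---|---|---|---|---|
| 99% | 106.1 | 23.7% | 72.5% | 84.4% | 96.2% |
| 99.5% | 93.55 | 13.4% | 82.3% | 89.0% | 95.7% |
| 99.9% | 83.51 | 3.0% | 92.1% | 93.6% | 95.2% |

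For example, at 99% with k = 0.5: (76.95 + 12.55) / 106.1 = 84.4%. The true value is 95% in every cell.

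**Comparison by symptoms.** Assume further that 30% of true and 85% of false positives report no symptoms, with 99% specificity.
- Without symptoms: TP = 24.3, FP = 21.335.
- With symptoms: TP = 56.7, FP = 3.765.
- k = 0: 23.085 / 45.635 = 50.6% without symptoms, against 53.865 / 60.465 = 89.1% with.
- k = 0.5: 33.7525 / 45.635 = 74.0% against 55.7475 / 60.465 = 92.2%.

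True persistence is 95% in both groups, so the whole difference is artefact.

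**With confirmation.** Assume a second assay with sensitivity 95%, specificity 99% and errors independent of the first. Confirmed TP = 81 × 0.95 = 76.95; confirmed FP = 25.1 × 0.01 = 0.251. With k = 0, observed persistence is 76.95 × 0.95 / 77.201 = 94.7%.

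The second assay also drops 81 × 0.05 = 4.05 true positives. If those were exactly the 4.05 who would lose antibody, the confirmed figure would rise to 76.95 / 77.201 = 99.7%. Confirmation removes most of the downward bias but can introduce an upward one.

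**The case against.** Five points can be made for the plan.

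- **A single test is not stated.** A reader might infer that one reactive result decides entry. The protocol does not say so: it is silent on the laboratory algorithm and does plan assay review and verification. This stands, and the point claims only that no confirmation step is named. The rest of Bias and limitations was not in the text at hand, so I do not claim that misclassification goes unacknowledged there.
- **The cohort is not everyone positive.** Positives are invited and must consent. This stands, but it removes the bias only if false positives decline far more often than true ones.
- **Low-incidence figures can be alarming.** For Sligo alone at 99% specificity with all false positives reverting, observed persistence is 8.55 / 18.9 = 45%. The protocol plans one proportion over serial participants and no split by area, so that figure does not describe a planned estimate.
- **Other information is planned.** The Objectives include antibody titres and function in positives, kinetics will be related to previous diagnosis, and stored sera may be retested. These could help to separate true from false positives, but none is tied to the persistence denominator.
- **The analysis plan may deal with it.** A misclassification adjustment could be there. But an analysis plan cannot use confirmatory results that the laboratory never generated, and the share of false positives that revert cannot be learned from this design.

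**Conclusion.** The concern holds in a limited form. The protocol names no confirmation step in its sampling, laboratory, retention or analysis text, and it fixes a measure that counts a reverting false positive as antibody loss. The proportion is likely to be too low unless false positives stay reactive.

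Under the stated assumptions the shortfall from a true 95% is about 11 to 22 points at 99% specificity, 6 to 13 at 99.5%, and 1 to 3 at 99.9% (half to all false positives reverting). If all stay reactive, the estimate is about 1 point too high at 99%.

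A reader might infer that the estimate will certainly be wrong. The documents do not support that: specificity, sensitivity, prevalence and reversion are all unstated, and with a very specific assay the bias is small. Nor should the effect on vaccination policy be overstated, because the Objectives tie that to age-specific susceptibility, which comes from the cross-sectional survey.

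**What to change.** Invitations need not change. Add to Laboratory testing and Data analysis:

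- Retest the stored baseline serum of each reactive participant on a second assay with a different antigen target.
- Test each person's baseline and follow-up samples on the same assay; if the assay changes, rerun the stored baseline serum on the new one.
- Report persistence among confirmed positives (second assay or previously confirmed diagnosis) alongside the all-positives figure, and show unconfirmed positives separately.
- Add a sensitivity analysis over specificity and over the share of false positives that revert.
- Use a restriction to previously diagnosed cases only as a sensitivity analysis, because it removes the undiagnosed infections that the study aims to capture.

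The cost is about 100 extra assays per round (84 to 106 across the specificities above), plus baseline reruns if the assay changes. Sera are kept for two years, consent to further antibody testing is already sought, and previous diagnosis is already collected. The downside is that the confirmed subset may lose weak true positives, perhaps those most likely to revert, so both figures should be reported.
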